6.1.2.2. Supplementary Analyses

To support the assessment of immunogenicity, estimands as specified in Section 2.2.4, using the treatment policy strategy, will be summarized with the mITT immunogenicity population using the same presentation (except the forest plots) as specified in the main analysis.

6.1.3. Local Reactions and Systemic Events for Substudy A

Analyses of reactogenicity endpoints are based on a subset of the safety population that includes participants with any e-diary data reported after each vaccination. Participants will be summarized by vaccine group as administered at each vaccination visit.

6.1.3.1. Main Analysis

- Estimand strategy: Treatment policy (Section 2.2.1.3.1).
- Analysis set: Safety population (Section 4).
- Analysis methodology: 95% CIs of the proportion of participants reporting each event will use the Clopper-Pearson method (Section 5.2.1).
- Intercurrent events and missing data: All data collected are included; partially missing diary data are imputed as "no" (Section 5.3.1.1); e-diary data that are confirmed as errors will not be used for analysis.
- Descriptive statistics, including the proportion (%), the numerator (n) and the denominator (N) used in the proportion calculation, and the 95% CI for percentage using the Clopper-Pearson method, will be presented for each vaccine group for each vaccination.
- Bar charts with the proportions of participants for each and any local reaction and each and any systemic event throughout the 7 days will be plotted for each vaccine group for each vaccination. The bars will be divided into severity categories to highlight the proportions of participants by maximum severity.

6.1.3.2. Supplementary Analysis

To support the assessment of reactogenicity, the following endpoints, as specified in Section 3.1.3.1, will be summarized per the supplemental analysis with the same analysis population:

- Duration (days) of each local reaction and each systemic event after vaccination.
- Onset day of each local reaction and each systemic event after vaccination.
- Presence of any local reaction and any systemic event on each of the 7 days, for the first 2 days (with nonmissing reactogenicity data from Day 1 through Day 2), first 3 days, first 4 days, first 5 days, first 6 days, all 7 days (nonmissing reactogenicity data for all 7 days), and for "any day (Day 1 through Day 7)."

The presentation of the results will include a basic descriptive summary without the 95% CIs (Section 5.2.1).

6.1.4. AEs for Substudy A

Participants will be summarized by vaccine group as defined in Section 3.1.3.3. All AEs after informed consent and prior to the first vaccination will not be included in the analyses but will be listed.

DMB02-GSOP-RF02 7.0 Statistical Analysis Plan Template 31-Jan-2022 PFIZER CONFIDENTIAL TMF Doc ID: 98.03 Page 38 of 46

6.1.4.1. Main Analysis

- Estimand strategy: Treatment policy (Section 2.2.1.3.2).
- Analysis set: Safety population (Section 4).
- Analysis methodology: 95% CIs of the proportion of participants reporting those events will use the Clopper-Pearson method (Section 5.2.1).
- Intercurrent events and missing data: All data collected are included.
- Descriptive statistics, including the proportion (%), the numerator (n) and the denominator (N) used in the proportion calculation, and the 95% CI for percentage using the Clopper-Pearson method, will be presented for each vaccine group for each analysis interval (Section 5.2.1).
- Bar charts with the proportions of participants for each variable within the specified interval will be plotted for each vaccine group for each analysis interval. The bars may be divided into relatedness categories to highlight the proportions of participants with related events.

6.1.4.2. Supplementary Analysis

To support the assessment of AEs, the following endpoints, as specified in Section 3.1.3.3, will be summarized with the same analysis population using the same presentation as specified in the main analysis:

- Immediate AEs after vaccination.
- Related AEs reported within 1 month after vaccination.
- Severe AEs reported within 1 month after vaccination.
- Life-threatening AEs reported within 1 month after vaccination.
- AEs leading to withdrawal reported within 1 month after vaccination.
- AESIs reported within 1 month after vaccination.
- SAEs reported within 1 month after vaccination.

6.1.5. SAEs for Substudy A

SAEs reported throughout the study will be summarized with the safety population using the same presentation as specified in Section 6.1.4.1.

6.1.6. Substudy B

The primary endpoints for Substudy B are the main safety endpoints, similar to Substudy A in Section 6.1.3, Section 6.1.4, and Section 6.1.5. The reactogenicity, AE, and SAE endpoints as described in Section 3.2.1 will be summarized with the safety population using the same presentation, as specified in Section 6.1.3, Section 6.1.4, and Section 6.1.5, respectively

6.2. Secondary Endpoint

No secondary endpoint is defined in the Substudy A.

6.2.1. Secondary Endpoints for RSV A– and RSV B–Neutralizing Antibody Titers for Substudy B

6.2.1.1. Main Analysis

- Estimand strategy: Hypothetical (Section 2.2.1.1).
- Analysis set: Evaluable immunogenicity population (Section 4).
- Analysis methodology: GMR, defined as the ratio of RSV A– and RSV B–neutralizing GMTs in the 2 combination (RSVpreF + qIRV) 1.0-mL and 0.5-mL groups at Visit B102 will be summarized along with the 95% CI (Section 5.2.2.3).
- Intercurrent events: Data collected after an intercurrent event will not be included (Section 2.2.1.1).
- Missing data: Missing data will not be imputed (Section 5.3.2).
- RSV A- and RSV B-neutralizing GMTs and sample size in the 2 combination groups at Visit B102 will be presented overall and by age group.
- GMRs and 95% CIs for the GMRs, using the Student t distribution, will be presented (Section 5.2.2.3) overall and by age group.

6.2.1.2. Supplementary Analysis

To support the assessment of immunogenicity, estimands, as specified in Section 2.2.3 using the treatment policy strategy, will be summarized with the mITT immunogenicity population using the same presentation as specified in the main analysis.

6.2.2. Secondary Endpoints for HAI Titers for Substudy B

6.2.2.1. Main Analysis

- Estimand strategy: Hypothetical (Section 2.2.1.2).
- Analysis set: Evaluable immunogenicity population (Section 4).
- Analysis methodology: GMR, defined as the ratio of HAI GMTs in the 2 combination (RSVpreF + qIRV) 1.0-mL and 0.5-mL groups at Visit B102 will be summarized along with the 95% CI (Section 5.2.2.3).
- Intercurrent events: Data collected after an intercurrent event will not be included (Section 2.2.1.2).
- Missing data: Missing data will not be imputed (Section 5.3.2).
- HAI GMTs and the sample size in the 2 combination groups at Visit B102 will be presented for each age group and overall.
- GMRs and 95% CI for the GMRs, using the Student t distribution, will be presented (Section 5.2.2.3) overall and by age group.

6.2.2.2. Supplementary Analyses

To support the assessment of immunogenicity, estimands, as specified in Section 2.2.3 using the treatment policy strategy, will be summarized with the mITT immunogenicity population using the same presentation as specified in the main analysis.

6.2.3. Other Endpoint(s)

The analysis in this section will be the same for Substudy A and substudy B.

6.2.3.1. Use of Antipyretic Medication Within 7 Days After Vaccination

The use of antipyretic medication within 7 days after vaccination will be summarized along with systemic events, except there is no severity grading. Onset and duration will also be summarized. Although it is included in the systemic events, use of antipyretic medication will not be considered as "any systemic event."

6.2.3.2. Immunogenicity as Measured by NTs and HAIs

Participants will be summarized by vaccine group according to the vaccine group to which they were randomized.

GMTs of NTs for each RSV subgroup (A or B) and RSV A/B combined, and GMTs of influenza strain-specific HAI titers at each applicable time point, will be descriptively summarized with 2-sided 95% CIs for each vaccine group.

GMFRs of NTs for each RSV subgroup (A or B) and RSV A/B combined, from before vaccination to each applicable postvaccination time point, and GMFRs of influenza strain-specific HAI titers from before vaccination to 1 month postvaccination, will be descriptively summarized with 2-sided 95% CIs for each vaccine group.

RCDC for each RSV subgroup (A or B) NTs at 1 month after RSVpreF (or combination) vaccination and RCDC for influenza strain-specific HAI titer at 1 month after qIRV (or combination) vaccination will be plotted for each group.

Analysis will be performed in the evaluable RSV immunogenicity population and evaluable HAI immunogenicity population.

6.2.4. HAI Seroprotection and Seroconversion

Descriptive statistics, including the proportion (%) of participants with seroprotection, seroconversion and the numerator (n) and the denominator (N) used in the proportion calculation, and the 95% CI for percentage using the Clopper-Pearson method, will be presented for each strain in each vaccine group at both Visit A101 and Visit A102 for seroprotection, and at Visit A102 for seroconversion, in the evaluable HAI immunogenicity population for SSA. Similarly, the summary will be provided at both Visit B101 and Visit B102 for seroprotection and at Visit B102 for seroconversion, in the evaluable immunogenicity population for SSB.

6.3. Subset Analyses

Substudy A. CC		
Substudy 11.		
Substudy B: O		
Substany 21		

6.4. Baseline and Other Summaries and Analyses

The analyses in this section will be the same for Substudy A and Substudy B.

6.4.1. Baseline Summaries

For each vaccine group, descriptive summary statistics for demographic characteristics (age at vaccination, sex, race, and ethnicity) and baseline information will be generated, as well as for all participants in total, based on the safety population.

Summary data will also be presented for the evaluable immunogenicity population(s).

Participant data listings for demography and baseline characteristics will also be generated.

Baseline blood pressure and pulse rate will be presented.

DMB02-GSOP-RF02 7.0 Statistical Analysis Plan Template 31-Jan-2022 PFIZER CONFIDENTIAL TMF Doc ID: 98.03 Page 42 of 46

6.4.2. Study Conduct and Participant Disposition

The number and proportion of randomized participants will be included in the participant disposition summary. In addition, participants who completed each vaccination, completed the study, and withdrew before each study visit, along with the reasons for withdrawal, will be tabulated by vaccine group and for all participants included in the randomized population. The reasons for withdrawal will be those as specified in the database.

Participants excluded from the evaluable and mITT populations will also be summarized with reasons for exclusion.

Participants with important protocol deviations from vaccination through the end of the study will be summarized among the safety population.

The e-diary completion rate will be summarized for the safety population, by vaccine group (in Section 3.1.3 for Substudy A and in Section 3.2.1 for Substudy B), as well as summarized with the categorized days specified in Section 3.5.3.

Standard listings will be generated, including but not limited to participants who withdrew during the study, participants excluded from analysis populations, and participants with important protocol violations.

6.4.3. Nonstudy Vaccines

Nonstudy vaccines recorded after signing the informed consent through the end of the study will be categorized according to the WHODrug Dictionary, and may be summarized by vaccine group and for all participants included in the safety population.

A listing may be used to replace the table.

6.5. Safety Summaries and Analyses

6.5.1. Adverse Events

For both SSA and SSB: For all of the AEs categorized in Section 3.1.3.3 and Section 3.1.3.4, each individual AE including SAE after vaccination will be categorized by the MedDRA PT and descriptively summarized with count, percentage, and 95% CI for vaccine group.

For Tier 1 events, the 2-sided 95% CIs for the difference in the percentage of participants reporting the events between the RSVpreF contained group and the control group will be calculated using the test statistic proposed by Miettinen and Nurminen³; in addition, the asymptotic p-values will also be presented for the difference in the percentage of participants reporting the events, based on the same test statistic and under the assumption that the test statistic is asymptotically normally distributed.

Because all participants enrolled in this study are expected to receive either RSVpreF or (RSVpreF+qIRV), there is no control in this study. Therefore, the intervention group will be all participants who received (RSVpreF+qIRV) or RSVpreF from both SSA and SSB, and the control group will be from RSVpreF pivotal Phase 3 study (C3671013) who received placebo only. The count for each Tier 1 event and denominator from C3671013 placebo group will be provided in this Tier 1 AE analysis.

It should be recognized that most studies are not designed to reliably demonstrate a causal relationship between the use of a pharmaceutical product and an AE or a group of AEs. Except for selecting events in unique situations, studies do not employ formal adjudication procedures for the purpose of event classification. As such, safety analysis is generally considered an exploratory analysis and its purpose is to generate hypotheses for further investigation.

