3.6. Safety Endpoints

3.6.1. Adverse Events

Guillain-Barre syndrome (from Day 1 through Day 43 after vaccination with RSVpreF or (RSVpreF+qIRV), where Day 1 is the day of vaccination), atrial fibrillation (from vaccination with RSVpreF or (RSVpreF+qIRV) through the Month 1 visit), and polyneuropathy (from Day 1 through Day 43 after vaccination with RSVpreF or (RSVpreF+qIRV), where Day 1 is the day of vaccination) have been identified as Tier 1 events for RSVpreF. The RSV program list of Tier 1 MedDRA PTs, maintained by the safety risk lead, is in the CAETeLiSt and is referenced in the safety surveillance review plan for the program. The current list of Tier 1 events should be confirmed to ensure that appropriate Tier 1 events will be used to produce final tables/graphs before conducting an analysis. Because RSVpreF is a vaccine component of the combination vaccine and is also study vaccine, these Tier 1 events are defined in this study.

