5.2.1. Analyses for Binary Data

Descriptive statistics for binary variables are the proportion (%) and the numerator (n) and the denominator (N) used in the proportion calculation. The 95% CI for percentage, and for the difference in percentages, will also be presented where applicable.

- 1. The 95% CI for the proportion (within vaccine group) will be constructed by the Clopper-Pearson method described by Newcombe.² The 95% CI will be presented in terms of percentage.
- 2. The 95% CI for the difference in the proportions (between vaccine groups) will be computed using the Miettinen and Nurminen method.³ The 95% CI will be presented in terms of percentage.

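### For very rare Tier 1 events the planned asymptotic p-value is too small: one case against 4 to 6 placebo cases (assumed counts) gives 0.010 to 0.038, where exact tests give 0.060 to 0.155

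*SAP*

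**What the plan says.** SAP 3.6.1 names three Tier 1 events: Guillain-Barre syndrome, atrial fibrillation and polyneuropathy. For these, SAP 6.5.1 plans a Miettinen-Nurminen 95% confidence interval for the difference in percentages. It adds that "the asymptotic p-values will also be presented for the difference in the percentage of participants reporting the events", and that these are "based on the same test statistic and under the assumption that the test statistic is asymptotically normally distributed".

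The intervention group pools everyone given RSVpreF, alone or combined, in both substudies. The comparator is external. The reason given is that "there is no control in this study", so placebo recipients of C3671013 are used: "The count for each Tier 1 event and denominator from C3671013 placebo group will be provided in this Tier 1 AE analysis".

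The section gives no exact alternative, no minimum count and no rule for an event with no cases. It does say that "safety analysis is generally considered an exploratory analysis and its purpose is to generate hypotheses for further investigation". SAP 5.1 states that neither substudy has a statistical hypothesis.

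**The concern.** A normal reference distribution needs a reasonable expected count in each group. Here the groups differ in size by about 41 to 1 (18,500 / 450). If the placebo arm had 5 cases, the expected intervention count under no difference would be 5 × 450 / 18,500 = 0.12. The intervention count is then almost always 0 and occasionally 1, which is far from normal.

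The p-value is the only significance measure attached to these prespecified safety events. A single chance case could be displayed with a p-value several times smaller than the data support, and the planned interval would exclude zero with it.

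**Working it through.** **Inputs.**
- Intervention n1 = 250 + 200 = 450, the planned enrolment (Protocol 1.1.1.3 and 1.1.2.3).
- Control n2 = 18,500, assumed: Protocol 2.2.3.1 gives over 37,000 participants randomized 1:1, but no arm size.
- Placebo event counts are not in the documents, so they are varied.
- The documents state no Tier 1 p-value, so there is no figure to reproduce.

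**Asymptotic p.** At zero difference the statistic is z = (p1 − p2) / √[p(1 − p)(1/n1 + 1/n2) · N/(N − 1)], with p the pooled rate and N = 18,950. For 1 versus 5 cases:
- p1 − p2 = 1/450 − 5/18,500 = 0.001952
- p = 6/18,950 = 0.000317
- standard error = 0.000849
- z = 2.30, two-sided p = 0.0215

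**Fisher's p.** Given 6 cases in all, the chance that at least one falls in the smaller group is close to 1 − (18,500/18,950)^6 = 0.134. The zero-case outcome is more probable than the one observed, so it adds nothing to the two-sided p.

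**Exact unconditional p.** Sum the probability of every table with |z| at least as large as observed, then take the maximum over the unknown common rate. The restricted version (Berger-Boos) searches only the 99.9% confidence interval for that rate and adds 0.001.

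| Cases: intervention vs placebo | Asymptotic | Unconditional | Restricted | Fisher |
|---|---|---|---|---|
| 1 vs 0 | <0.0001 | 0.009 | 0.010 | 0.024 |
| 1 vs 1 | <0.0001 | 0.020 | 0.021 | 0.047 |
| 1 vs 2 | 0.0004 | 0.033 | 0.034 | 0.070 |
| 1 vs 3 | 0.003 | 0.046 | 0.047 | 0.092 |
| 1 vs 4 | 0.010 | 0.060 | 0.061 | 0.113 |
| 1 vs 5 | 0.021 | 0.075 | 0.076 | 0.134 |
| 1 vs 6 | 0.038 | 0.089 | 0.090 | 0.155 |
| 1 vs 7 | 0.060 | 0.104 | 0.105 | 0.175 |
| 1 vs 10 | 0.143 | 0.147 | 0.148 | 0.232 |
| 10 vs 200 | 0.022 | 0.075 | 0.023 | 0.035 |

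**Confidence interval.** At 1 versus 4, 5 and 6 the planned interval runs from 0.015% to 1.23%, 0.009% to 1.22% and 0.003% to 1.22%, each excluding 0. Inverting the (unrestricted) exact unconditional test gives −0.003% to 1.30%, −0.008% to 1.29% and −0.013% to 1.29%, each including 0.

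**Actual size.** With no true difference, the asymptotic test's maximum rejection rate is 0.089 at nominal 0.05 (about 5 cases expected in total), 0.060 at 0.01 and 0.033 at 0.001. With 10 or more expected in total, the size at nominal 0.05 lies between about 0.038 and 0.061.

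**Sensitivity to the denominators.** With 405 versus 18,500, both exact tests exceed 0.05 while the asymptotic p does not at 4 to 7 placebo cases. With 450 versus 17,000 this happens at 3 to 5.

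**No events.** With no case in either group, z is 0/0.

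**The control statement.** SAP 3.6.1 sets the window as "atrial fibrillation (from vaccination with RSVpreF or (RSVpreF+qIRV) through the Month 1 visit", but as "Guillain-Barre syndrome (from Day 1 through Day 43 after vaccination with RSVpreF or (RSVpreF+qIRV" for Guillain-Barre syndrome, with the same Day 43 limit for polyneuropathy. Substudy A Group 2 receives only qIRV until Vaccination 2, 28 to 35 days later (Protocol 10.9.10.6.2). The table in SAP 3.1.3 already derives adverse events from Vaccination 1 to before Vaccination 2 for both the combination and the qIRV-alone groups. For atrial fibrillation this is a concurrent randomized contrast. For the other two events the window runs past the day Group 2 receives RSVpreF, so the SAP's statement stands.

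**The case against.** The strongest reply is that nothing depends on 0.05. There is no hypothesis or threshold, the normality assumption is stated openly, the counts and denominators appear beside the p-value, and the analysis is labelled exploratory. A safety screen may also prefer sensitivity. All of this stands and limits the impact. It does not make the displayed number correct.

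A second reply is that an exact remedy can do harm, and this also stands for one version. The unrestricted unconditional test takes its maximum at a few expected events even when far more were observed. At 10 versus 200 it gives 0.075 although the asymptotic 0.022 is sound. Restricting the rate removes the problem (0.023).

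Third, Protocol 9.3.1.1 specifies the Miettinen-Nurminen interval, and SAP 2.1 declares no change from the protocol. That is a good reason to keep the planned interval.

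Fourth, SAP 6.5.1 already tabulates each event by vaccine group, so only the difference for atrial fibrillation is missing. That is so. SAP 5.2.1 allows it ("The 95% CI for percentage, and for the difference in percentages, will also be presented where applicable") but does not specify it for this event.

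A reader might infer that the same reversal holds with two or three intervention cases. The restricted test does not support that: it gives 0.043 at 2 versus 15 and 0.032 at 3 versus 33, so the reading there depends on the exact test chosen. Nor is Fisher's test always the more conservative: at 10 versus 200 it gives 0.035 against 0.075 for the unrestricted test.

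**Conclusion.** The point holds for very rare Tier 1 events and is a matter to consider, not a defect in the main analyses. With one intervention case and 4 to 6 placebo cases, the planned p-value is below 0.05 and both exact tests are above it. With 2 or 3 placebo cases the planned p-value is far too small, but which side of 0.05 is right depends on the exact test. With 0 or 1, both exact tests are also below 0.05.

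This rests on about 450 and 18,500 participants and on assumed counts. A reader might infer that all Tier 1 p-values are unreliable. The documents do not support that: they give no event counts, and an event that proves common would not be affected.

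A reader might also infer that the SAP is wrong to say the study has no control. That is so only for atrial fibrillation. An exact p-value does not address the fact that the main comparator is external and non-concurrent.

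**What to change.** 1. In SAP 6.5.1, keep the Miettinen-Nurminen interval. For each Tier 1 event, present an exact p-value in place of, or beside, the asymptotic one. Use either Fisher's test or the exact unconditional test on the same score statistic, with the common rate limited to its 99.9% confidence interval and 0.001 added (Berger-Boos). Do not use the unrestricted maximisation.
2. Where the expected intervention count is small (cut-off to be stated in advance), add the matching exact interval or a note that the planned lower limit is unreliable.
3. Report no p-value when neither group has an event.
4. Separately, for atrial fibrillation only, qualify the no-control sentence. Show the Substudy A Group 1 minus Group 2 difference, from Vaccination 1 to before Vaccination 2, with its 95% interval and a note on its low precision.

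**Cost.** SAP wording, a routine computation and some sensitivity at very low counts. With a true rate ratio of 5 and 3 expected placebo cases, the chance of p<0.05 is 30% asymptotic, 22% exact unconditional and 10% Fisher. With 5 expected it is 38%, 21% and 14%. Part of the asymptotic advantage is inflated size: with no true difference it gives p<0.05 in 6.8% and 8.9% at those counts, against 4.6% and 3.5% for the exact unconditional test. The randomized atrial fibrillation contrast is weak: at 125 per group, 5 versus 0 gives Fisher p = 0.060 and 6 versus 0 gives 0.029.

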C3671013 is an ongoing Phase 3, multicenter, randomized, double-blind, placebo-controlled study to assess the safety, immunogenicity, and efficacy of Pfizer's RSVpreF in prevention of RSV-associated LRTI in adults 60 years of age and older. Both healthy adults and adults with stable chronic cardiopulmonary conditions are included. Approximately 10% of participants with stable chronic cardiopulmonary conditions such as COPD, asthma, or CHF are being enrolled. The study enrolled over 37,000 participants, randomized to receive RSVpreF or placebo in a 1:1 ratio. This is an event-driven study with a target of 59 first episodes of evaluable RSV-associated LRTI cases. Interim analysis results in August 2022 showed protection against LRTI-RSV defined by 2 or more symptoms demonstrated vaccine efficacy. 66.7%. Vaccine efficacy of 85.7% was observed in participants with a more severe disease primary endpoint of LRTI-RSV defined by analysis of 3 or more RSV-associated symptoms. The vaccine was well tolerated, with no safety concerns.

C3671006 is a Phase 3, multicenter, parallel-group, placebo-controlled, randomized, double-blind study. 1403 healthy adults ≥65 years of age were randomized 1:1 to either a coadministration group or a sequential-administration group. The intention of this study was to demonstrate that the immune responses generated when a 120-µg RSVpreF dose was coadministered with SIIV were noninferior to the immune responses when these products were administered 4 weeks apart. The safety and tolerability of RSVpreF were also examined. Results demonstrated noninferiority of the RSVpreF and SIIV immune responses when RSVpreF was coadministered with SIIV. The results of this study support the acceptability of coadministration of RSVpreF and SIIV in an older adult population.

RSVpreF is also being studied in the maternal program, which includes Phase 2b and Phase 3 studies in pregnant women and a Phase 2b study in nonpregnant women. Details of each of these studies are provided in the RSVpreF IB.

2.2.3.2. qIRV

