Systemic events within 7 days after vaccination	Systemic events reported within 7 days after Vaccination 1 among participants who received the combination vaccine at Visit A101 with at least 1 day of e-diary data transferred following the vaccination.	Systemic events reported within 7 days after Vaccination 1 or after Vaccination 2 among participants who received qIRV at Visit A101 with at least 1 day of e-diary data transferred following vaccination and received RSVpreF at Visit A102 with at least 1 day of e-diary data transferred following vaccination.	Systemic events reported within 7 days after Vaccination 1 among participants who received qIRV at Visit A101 with at least 1 day of e-diary data transferred following the vaccination.	Systemic events reported within 7 days after Vaccination 2 among participants who received RSVpreF at Visit A102 with at least 1 day of e-diary data transferred following the vaccination.	Systemic events reported within 7 days after Vaccination 2 among participants who received placebo only at Visit A102 with at least 1 day of e-diary data transferred following the vaccination.
AEs within 1 month after vaccination	AEs reported from Vaccination 1 to before Vaccination 2 among participants who received the combination at Visit A101.	AEs reported from Vaccination 1 throughout the study among participants who received qIRV at Visit A101 and RSVpreF at Visit A102.	AEs reported from Vaccination 1 to before Vaccination 2 among participants who received qIRV at Visit A101.	AEs reported from Vaccination 2 through the end of the study among participants who received RSVpreF at Visit A102.	AEs reported from Vaccination 2 through the end of the study among participants who received placebo only at Visit A102.
SAEs throughout the study	SAEs reported from Vaccination 1 throughout the study among participants who received the combination at Visit A101.	SAEs reported from Vaccination 1 throughout the study among participants who received qIRV at Visit A101.	N/A	N/A	N/A

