5. GENERAL METHODOLOGY AND CONVENTIONS

5.1. Hypotheses and Decision Rules

There is no statistical hypothesis in Substudy A and Substudy B.

The estimands corresponding to each primary, secondary, or exploratory objective are described in Section 2.2.

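### SAP 6.5.1 says there is no control for Tier 1 events, but month 1 of Substudy A has a randomised qIRV-alone group; the only planned difference mixes RSVpreF, qIRV, age and study effects

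*SAP*

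**What the plan says.** SAP Section 3.6.1 names three Tier 1 events for RSVpreF. Guillain-Barré syndrome and polyneuropathy are counted from Day 1 through Day 43 after an RSVpreF-containing vaccination. The third is "atrial fibrillation (from vaccination with RSVpreF or (RSVpreF+qIRV) through the Month 1 visit".

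Section 6.5.1 specifies "the 2-sided 95% CIs for the difference in the percentage of participants reporting the events between the RSVpreF contained group and the control group", by the Miettinen-Nurminen method, with asymptotic p-values. It then states that "Because all participants enrolled in this study are expected to receive either RSVpreF or (RSVpreF+qIRV), there is no control in this study". On that basis "the intervention group will be all participants who received (RSVpreF+qIRV) or RSVpreF from both SSA and SSB". The comparator is taken from outside the trial: "the control group will be from RSVpreF pivotal Phase 3 study (C3671013) who received placebo only".

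Elsewhere the SAP describes a different situation for Substudy A. Section 2.3.1 randomises about 250 adults 1:1 to the combination at Visit A101 (Group 1) or to qIRV at A101 followed by RSVpreF at A102 (Group 2). The endpoint table in Section 3.1.3 has a column for qIRV alone, covering "AEs reported from Vaccination 1 to before Vaccination 2 among participants who received qIRV at Visit A101". The combination column uses the same interval.

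**The concern.** The premise of the sentence is true over the whole study, because everyone is expected to receive RSVpreF eventually. The conclusion does not follow for the first month of Substudy A. Until A102, Group 2 has had no RSVpreF, and it was randomised alongside a group that has.

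The Tier 1 list belongs to RSVpreF, so a reader will take the planned difference as evidence about RSVpreF. Yet qIRV exposure is universal on one side and absent on the other. The documents themselves make a qIRV contribution plausible for atrial fibrillation. Protocol Section 2.3.1 says the myocarditis and pericarditis risk seen with mRNA COVID-19 vaccines could extend to influenza modRNA vaccines. The stopping rule in Protocol Section 10.9.10.5.1 lists sustained atrial arrhythmia among the ECG findings a cardiologist may judge consistent with those conditions. An excess over the external placebo arm could be credited to the wrong component, with no between-group estimate beside it that holds qIRV constant.

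**Working it through.** The documents give no sample size, power or precision for the Tier 1 contrast, so there is no stated figure to reproduce.

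**Exposure count** (planned sizes from SAP Sections 2.3.1 and 2.3.2):

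- Substudy A combination: 125, qIRV in the same injection.
- Substudy B combination, both formulations: 200, qIRV in the same injection.
- Substudy A RSVpreF at A102: 125, qIRV given 28-35 days earlier.
- Total: 125 + 200 + 125 = 450. Same-injection exposure: 325/450 = 72%. Any prior or simultaneous qIRV: 450/450.

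The external control received placebo only, in a trial for "prevention of RSV-associated LRTI in adults 60 years of age and older" (Protocol Section 2.2.3.1). Substudy B enrols from age 50, so it adds some participants under 60. The plan fixes about 100 aged 50-64 but does not say how many are under 60.

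**What each contrast estimates:**

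- External: RSVpreF effect + qIRV effect + differences of age and study.
- Internal (combination minus qIRV alone, month 1 of Substudy A): the effect of adding RSVpreF to qIRV, among people randomised at the same time.

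Illustration under an assumed qIRV effect of +1 percentage point, no RSVpreF effect and no age or study difference. The external contrast is centred on 325/450 × 1 = 0.72 points if nothing carries over to the 125 vaccinated a month later, and on 1.0 point if all of it does. The internal contrast is centred on 0.

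**Window covered by the qIRV-only period** (28-35 days by the visit schedule):

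| Event | SAP window | Covered |
|---|---|---|
| Atrial fibrillation | to Month 1 visit | all |
| Guillain-Barré syndrome | Days 1-43 | 28/43 to 35/43 = 65% to 81% |
| Polyneuropathy | Days 1-43 | 65% to 81% |

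**Precision of the internal contrast.** The Miettinen-Nurminen limits solve

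z² = (p1 − p2 − d)² / {[q1(1 − q1)/n1 + q2(1 − q2)/n2] × N/(N − 1)} = 1.96²,

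where q1 and q2 are the maximum likelihood estimates restricted to q1 − q2 = d. With no events in either group the upper limit has q1 = d and q2 = 0, so

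d/(1 − d) = 3.8415 × 250/(249 × 125) = 0.03086, giving d = 2.99 points.

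By symmetry the interval is -2.99 to +2.99. Solved numerically, 1 against 0 events gives -2.21 to +4.40, and 2 against 1 gives -2.95 to +4.95.

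Background rates are not given. For assumed qIRV-alone rates of 0.1%, 0.5%, 1% and 2%, the combination rate would have to reach about 6.3%, 7.3%, 8.5% and 10.6% for 80% power at 125 per group (normal approximation, rough at these counts).

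**Precision of the external contrast, for comparison.** C3671013 enrolled over 37,000 participants 1:1; assume half of 37,000, so 18,500 on placebo. With no events on either side, 450 against 18,500 gives -0.02 to +0.85 points.

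**The case against.** The SAP does not claim to isolate RSVpreF. It speaks of a group whose vaccine contains RSVpreF, describes safety analysis as generally exploratory, and states that "There is no statistical hypothesis in Substudy A and Substudy B". The primary safety objective concerns the combination itself. For rare events, screening recipients against a large placebo arm is a defensible choice, and the external interval is far narrower than the internal one. All of this stands, and it is why the external contrast should be kept.

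A reader might infer from the no-control sentence that the month-1 qIRV-alone data go unreported. The documents do not support that. The opening paragraph of SAP Section 6.5.1 summarises individual events by preferred term with counts, percentages and intervals for each vaccine group, and Section 3.1.3 makes qIRV alone and the combination separate groups over the same interval. Only the difference between them is missing.

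A reader might also take the qIRV-alone month as a full control for all three events. It is that only for atrial fibrillation. For the two Day 43 events it cannot be extended, because Group 2 then receives RSVpreF.

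Two further limits apply. The internal contrast sets a 1-mL injection against a 0.5-mL one (Protocol Sections 10.9.8.1.1 and 10.9.8.1.2). At 125 per group it will rarely settle anything about a rare event. These limits make it a supplement; they do not make the statement that no control exists correct.

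**Conclusion.** The point holds as one incorrect statement and one missing estimate. SAP Section 6.5.1 should not say the study has no control, because Substudy A provides about 125 randomised, concurrent participants unexposed to RSVpreF for 28-35 days. The planned external difference compares about 450 qIRV-exposed participants with placebo recipients from another trial and cannot be read as the effect of RSVpreF.

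It would be tempting to put a number on the age bias, or to treat all of the roughly 100 participants aged 50-64 as outside the C3671013 age range. The documents allow neither: those aged 60-64 are within that range, the number under 60 is not stated, and no age-specific event rates are given. Nor can the internal contrast replace the external one, with an interval of about ±3.0 points at 0 against 0.

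The conclusion rests on the planned group sizes and the scheduled visit interval. The 0.72 to 1.0 point illustration depends on an assumed qIRV effect.

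**What to change.** 1. Delete or qualify the no-control sentence in SAP Section 6.5.1, stating that Group 2 of Substudy A is unexposed to RSVpreF until Vaccination 2.
2. Add, as a descriptive supplement, the Substudy A combination minus qIRV-alone difference for each Tier 1 event, from Vaccination 1 to before Vaccination 2, with the Miettinen-Nurminen 95% interval. Label the Guillain-Barré syndrome and polyneuropathy rows as truncated at Vaccination 2 (28-35 of 43 days), and footnote the difference in injection volume.
3. Keep the C3671013 contrast and add a version limited to participants aged 60 and older. State that both versions estimate receipt of both vaccines versus placebo across studies, not the effect of RSVpreF alone.

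The cost is SAP wording and a few table rows from data already collected and intervals already defined. The downside is a wide internal interval, possibly 0 against 0, which must be presented as descriptive so that it is not read as reassurance.
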